### 14.3 Procedure for Dealing with Missing, Unused and Spurious Data

Outliers will remain within the data. Within the data analysis software missing data will be coded 9999 and the data point missed during analysis.

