### *Intervention*

[figure not shown]
Participants will undertake 10 days of moderate home-based overnight normobaric hypoxia (FIO2 = ~0.155), and a sham hypoxia intervention (FIO2 = 0.2093) using hypoxic 'pillow tents' in a random order. The use of pillow tents rather than whole body tents was based on patient and public involvement (PPI) consultations. Participants will wear an SpO2 monitor at all times within the tent that will sound an alarm if SpO2 falls too low. If it sounds, participants will remove the hood (so that they breathe ambient air) and leave it off for the remainder of the night. An independent medical officer will decide if the participants can remain in the trial. The O2 fraction will be set by the researcher and participants instructed not to change the settings. Finally participants will be asked to maintain a diary of the time spent in the tent. Finally, participants will be asked to record a dietary diary and photograph meals in order to try and replicate it in both conditions. Participants will then undertake the alternative condition. The cross-over conditions will be separated by a minimum 4 week wash out period. During the intervention, as well as recording safety information (ie. SpO2) we will ask participants to wear a continuous glucose monitor (CGM) sensor (Abbott Diabetes Care Inc., Alameda, CA, USA) on the anterior portion of the upper arm with a small adhesive patch. These sensors will be worn for 14 days to determine free-living glycaemic control, in addition to a wrist-worn accelerometer (GENEActiv, Activinsights, Kimbolton, Cambridge, UK) to assess baseline habitual physical activity (PA) and sleep [32] (see details below in section 10.4).

*Visit 2, 3, 4 and 5 (approx 2.5 per visit)*

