#### **13.2 Data Management**

All study data (excluding electronic files) will be entered on paper copies and stored in participant CRF's. Electronic files will be stored on a shared (with access restricted to only the research team) google drive. All data will be double data entered into excel. Macro's will be used to check for anomalies and corrected. The participants will be identified by a study specific participants number and/or code in any database. The name and any other identifying detail will NOT be included in any study data electronic file. The chief investigator ([name]) is responsible for database maintenance and management.

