## 14. DATA ANALYSIS

### 14.1 Description of Analysis Populations

All participants who complete all visits will be entered into the analysis as per protocol.

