### 14.2 Analysis of Endpoints

All data will be tested for normality using the Shapiro-Wilk test. For normally distributed data, paired samples t-tests will be used to assess differences pre and post hypoxic exposures for; blood [glucose] (AUC and peak), insulin sensitivity, eHSP70, IL-6, leptin, ghrelin, TNFa, SOD, HIF-1 $\alpha$  HR, PA and sleep efficiency. For non-parametric data Wilcoxon-Signed rank test will be used for pairwise comparisons. Repeated measures one-way analysis of variance (ANOVA) will be used to identify differences between conditions for SpO2 and [glucose] across time from the CGMs. Mauchly's test of sphericity will be used to determine if any data violated the assumption of spherical data. If violated, sphericity will be accounted for using the Greenhouse-Geisser correction. Where significant differences are observed ( $P < 0.05$ ), post-hoc tests will be performed using LSD pairwise comparisons. Effect sizes will be reported as partial eta squared ( $\eta^2_p$ ) (small = 0.01; medium = 0.06; large = 0.14) [33].

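### The rule that a missing point is skipped does not fit the repeated-measures ANOVA named for SpO2 and CGM glucose, and neither series has a time unit or an artefact rule

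*Combined protocol and SAP*

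**What the plan says.** Section 14.2 names the method for the two device series: "Repeated measures one-way analysis of variance (ANOVA) will be used to identify differences between conditions for" SpO2 and CGM glucose over time. It adds "Mauchly's test of sphericity will be used to determine if any data violated the assumption of spherical data" and then "If violated, sphericity will be accounted for using the Greenhouse-Geisser correction", with LSD comparisons after a significant result. It does not say whether a time point is a minute, an hour, a night, a day or a whole period.

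Section 14.3 gives the missing-data rule, "Within the data analysis software missing data will be coded 9999 and the data point missed during analysis", and the rule for extreme values, "Outliers will remain within the data".

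Three other places bear on this:

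- Section 14.1 defines the analysis set by visits: "All participants who complete all visits will be entered into the analysis as per protocol". It has no rule for a participant who attends every visit but lacks a night or a day of recording.
- Section 13.2, after describing double data entry, says "Macro's will be used to check for anomalies and corrected".
- Section 10 (Intervention) says that after a low-saturation alarm "participants will remove the hood (so that they breathe ambient air) and leave it off for the remainder of the night".

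Section 10.4 sets a minimum wear time for the accelerometer. It gives no comparable validity rule for the oximeter or the CGM sensor. Section 14.4 says that no further SAP is needed.

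**The concern.** Skipping a data point and running a classical repeated-measures ANOVA are incompatible instructions. The ANOVA and Mauchly's test work on complete rows, so an empty cell is resolved by deleting the participant. The plan does not say this will happen, and section 14.1 does not cover it.

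Gaps are likely in unattended home recordings, and they may not be random. The alarm rule shortens the nights of those who desaturate most. If shortened nights were treated as missing, the SpO2 analysis would lean towards participants who tolerate hypoxia well. Daily glucose excursions from CGM are a listed secondary outcome, and recorded SpO2 is used in section 11.2 to confirm exposure.

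The outlier rule raises a separate problem. Section 14.3 is headed as covering spurious data, but its only instruction on extreme values is to keep them. Read literally, an oximeter drop-out or a CGM fault is analysed as a true reading.

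**Working it through.** The plan gives no missing-night rate, number of time levels or expected number of complete records, so there is no figure of its own to reproduce.

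**Inputs from the documents.** 23 participants and 15% drop-out (section 2); 10 nights per condition, so 20 in all (section 10); 14 days per CGM sensor (section 10.4), so 28 over two periods if all days are used.

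**Assumption.** Each night or day is lost independently with probability p. The documents do not give p; 2%, 5% and 10% are shown.

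**Step 1: can the ANOVA skip a point?** A repeated-measures ANOVA was run on simulated data for 13 participants at 10 times (130 cells). With one row absent, the procedure stopped because the data were unbalanced. With one cell blank, it returned no F value. It runs only if that participant is deleted.

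**Step 2: complete records.** Expected completers = 23 × 0.85 = 19.55. Expected complete records = 19.55 × (1 − p)^K.

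| Loss per night or day | K = 20 nights | K = 28 CGM days |
|---|---|---|
| 2% | 19.55 × 0.668 = 13.1 | 19.55 × 0.568 = 11.1 |
| 5% | 19.55 × 0.358 = 7.0 | 19.55 × 0.238 = 4.7 |
| 10% | 19.55 × 0.122 = 2.4 | 19.55 × 0.052 = 1.0 |

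**Step 3: how far independence matters.** If loss clusters within people, fewer people carry it. Under a beta-binomial model for the 20 nights, an assumed intraclass correlation of 0.1 leaves about 16, 11 and 6 complete records at 2%, 5% and 10% loss. A correlation of 0.3 leaves about 17, 15 and 11.

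**Step 4: Mauchly's test.** For an effect with k levels it needs a full-rank (k − 1) × (k − 1) contrast covariance matrix. That matrix has rank at most n − 1, so n must be at least k.

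- 10 nights in a 2 × 10 layout: at least 10 complete cases.
- 14 CGM days in a 2 × 14 layout: at least 14.
- A single 20-level factor: at least 20. With 19 cases the rank is 18 against 19, which is singular; with 20 it is full.

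With 19 completers and independent loss, the binomial probability of too few complete cases is:

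| Loss | 2 × 10 nights (fewer than 10) | 2 × 14 CGM days (fewer than 14) |
|---|---|---|
| 1% | 0.1% | 32% |
| 2% | 6% | 90% |
| 5% | 90% | about 100% |

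With no loss, the 10-level test is computable for 13, 19 or 23 participants. If time points are finer than complete cases are numerous, it is never computable.

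**Step 5: is a simple mixed model a safe replacement?** Simulation with no true effect, 19 participants, 10 nights per condition and two-sided 5% tests. The mixed model has only a participant random intercept, with condition and night fixed.

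| Variation added | Participant intercept only | Paired test on condition means |
|---|---|---|
| Participant-by-condition SD 0.3 of the night SD | about 15% false positives | about 5% |
| Participant-by-condition SD 0.5 of the night SD | about 27% | about 5% |
| Night-to-night autocorrelation 0.3 | about 15% | about 5% |

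**The case against.** The strongest reply is that a nightly analysis is not in the text. If each participant contributes one summary per condition, a lost night removes nobody and sphericity does not arise. This stands as a limit on the size of the problem. It does not clear the plan: an analysis over time with Mauchly's test, a Greenhouse-Geisser correction and post-hoc comparisons has no use for two means, so section 14.2 or section 14.3 needs editing on either reading.

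A reader might infer four stronger things that the documents do not support.

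- *That the sphericity step cannot be carried out at all.* Steps 3 and 4 show that this depends on the layout and the loss rate.
- *That alarm nights are missing nights.* Section 10.4 says the oximeter stores its data, so a part-night record exists. Removing the hood does not interrupt a sensor on the arm, so the alarm rule gives no reason for CGM loss.
- *That mean SpO2 will be pulled down by a known amount.* No artefact rate or level is given. Very low readings would also meet the 65% alarm in section 10.4 and could end the night rather than accumulate. Artefact that is similar in both conditions would largely cancel within a person.
- *That sections 13.2 and 14.3 flatly contradict each other.* Section 13.2 follows double entry and reads as entry checking. The boundary with section 14.3 is undrawn, which is a smaller fault.

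It is also fair that SpO2 is not a listed outcome, that CGM is one of many secondary outcomes, and that the study calls itself a pilot.

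**Conclusion.** The concern holds in limited form. The point-wise missing-data rule cannot be applied to the ANOVA named for SpO2 and CGM glucose if that ANOVA is run on nights or days. The participant would be lost instead, and the plan does not say so. The time unit is undefined, and no artefact rule exists for either device.

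The counts of 13, 7 and 2 complete records rest on 20 nights, 19.55 completers and independent loss at assumed rates. They illustrate sensitivity and do not forecast the trial. Mauchly's test may become non-computable, and always does when time levels exceed complete cases.

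The paired tests are untouched: where a pair is missing, leaving it out works, and that includes the primary OGTT glucose AUC. The change should be made, but the primary result does not depend on it.

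**What to change.** In sections 14.2 and 14.3:

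1. State the time unit: nightly SpO2 and a daily CGM summary.
2. Compare conditions in one of two ways, chosen in advance. The simpler is a paired test on each participant's condition mean over the available nights or days. The other is a linear mixed model with condition, period and night (or day) as fixed effects, participant and participant-by-condition (period) random effects, autocorrelated residuals within period, and Kenward-Roger degrees of freedom. A participant random intercept alone should not be used, for the reason shown in step 5.
3. Keep part-night records, and report the number of alarm-ended nights by condition.
4. Remove device artefacts by a prespecified signal-quality rule applied blind to condition, and keep all genuine values.
5. Say where the anomaly correction in section 13.2 ends and the outlier rule in section 14.3 begins.

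The cost is revised wording, some extra data processing and, if the mixed model is chosen, a slightly more complex analysis. No new data are needed and trial conduct does not change.

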### 14.4 Procedures for Reporting any Deviation(s) from the Original Statistical Analysis Plan

For this pilot a SAP is not required (excluding the above).

### 14.5 Interim analysis and criteria for early study termination

Given the small samples size and time frame, no interim analysis will be performed. Early termination will only occur if the safety of participants is in question.

## 15. THICS

NHS Local Research Ethics Committee (REC) approval will be obtained prior to commencement of the study. The REC, local NHS, research and development department and all site specific forms and patient identification centre forms will be forwarded to the funder prior to recruitment of participants. Written informed consent will be obtained from all participants. Insurance indemnity will be provided by the Sponsor for this study.

Every effort has been made to keep the risks and discomforts to a minimum but there are some risks associated to taking part. Not all volunteers will experience any or all of the risks stated below, but participants will be made aware of them.

1. The main burden to you will be a lifestyle alteration because you will be asked to sleep in a tent for 2, 10 day periods whilst wear smart monitors. During these periods you will also be collecting urine samples and recording your food consumption in diaries.
2. We will also take small blood samples which can cause pain for a short period. Likewise, putting the glucose monitors on can cause mild discomfort.
3. The body composition scan involves a mild dose of radiation. All scans in this study (per participant) would be equivalent to 3 day of natural background radiation. It is, however, the most accurate and appropriate way of assessing the changes in your body across the intervention.

### 15.1 Participant Confidentiality

The study staff will ensure that the participants' anonymity is maintained. The participants will be identified only by initials and a participants ID number on the CRF and any electronic database. All documents will be stored securely and only accessible by study staff and authorised personnel. The study will comply with the Data Protection Act which requires data to be anonymised as soon as it is practical to do so.

### 15.2 Other Ethical Considerations

N/A

### 15.3 Declaration of Helsinki

The study protocol will be carried out in accordance with the declaration of Helsinki.

### 15.4 ICH Guidelines for Good Clinical Practice

All staff will be GCP trained and will be monitored by the sponsor to ensure adherence to GCP.

## **16. PATIENT PUBLIC INVOLVEMENT (PPI)**

### 16.1 Study design

Evidence of patient, carer and public involvement (PCPI):

The chief investigator has a strong track record of PCPI work having been involved in PCPI award winning projects from the UK Stroke Forum (2016) for an acceptability and feasibility trial. We have a PCPI co-applicant ([name]) who has been instrumental in the design and development of this study and will continue to be involved in the reporting, dissemination and future NIHR funding bids. Other individuals with T2DM have been consulted and have stated that they would prefer hoods rather than full tent coverings. Questions surrounding the smart technology were made following reviewing the PIS and pictures of the technology have been added. The lay summary and patient facing documentation has been reviewed by our PCPI co-applicant.

### 16.2 Study implementation

This is a pilot study and as such we do not have a TSC or DMC. Issues will be managed by the senior members of the research team. We will endeavor to involve the PCPI member where possible on decisions regarding the study and data.

### 16.3 Dissemination

Our PCPI member will help disseminate findings through local groups, local/national media, and co-authoring the paper. Our PCPI involvement has developed the protocol to this stage and will continue to play a large role in this project and the larger definitive trial to come.

**17. FINANCING AND INSURANCE**

Total funds are **\$120,000**. The full economic cost for this study is **\$170,166**. Public liability and indemnity insurance is covered by the University of Portsmouth.

17.1 Research Costs

*Total cost (\$120,000)*

Total funds funded are **\$120,000**. In order to keep the cost within the maximum budget the University of Portsmouth have only requested 11% (*\$13,013*) of the available 15% overhead costs. The full economic cost for this study is **\$170166**. Please see table 1 for the overview and text below for the detailed justification.

Table 1. Shows the breakdown of the study costs.

Breakdown of costs	Full economic costing (\$)	Funded (\$)
Research Associate 0.7fte	41402	41402
Recruitment	725	725
Consumables and Analysis	40933	40933
Small equipment	12843	12843
Participant travel	653	653
Publication Costs	2175	2175
PI [name] 2 hrs p/w (88 hrs)	5406	5388
CoI [name] 0.34 hrs p/w (2 days)	922	919
CoI [name] 0.34 hrs p/w (2 days)	1103	1099
CoI [name] 0.17 hrs p/w (1 day)	853	850
Infrastructure technician	2024	0
Estates Costs	15408	0
Indirect Costs	45719	13013

Total (\$)	170166	120000
-------------------	---------------	---------------

\$ displayed are USD.

*Value added to the project*

The Extreme Environments Laboratory at the University of Portsmouth has a 30 year history of conducting innovative human research trials. The laboratory contains some of the world's leading facilities for conducting environmental research including three bespoke environmental chambers, with temperature, humidity, solar, wind and hypoxia control, and a research group involving over 20 academics and researchers. The Institute of Biological and Biomedical Sciences at the University of Portsmouth has state of the art laboratories to enable us to analyse our biological samples. As well as the bespoke chambers, it hosts portable kit essential for this study such as two hypoxic generators (cloud 9), SpO2 monitors (Equivital EQ02, Hidalgo, UK) and accelerometers.

*Researcher time (total = \$80,536)*

We request funds for an experienced researcher (senior research associate) in order to achieve the timeline goals (12 months, full-time = \$71,555). They will assist with the day to day running of the project, including participant recruitment, study logistics, data collection, inputting and analysis (including biochemistry). We will need \$725 for recruitment purposes (to ensure we get the correct candidate and advertise to the largest audience). Academic staff time for this grant totals \$8,256.

*Equipment (total = \$12,843)*

We will buy two hypoxic systems (cloud 9), and individual pillow tents (tents are not transferable between individuals for hygiene reasons and are considered a consumable) from Sporting Edge UK Ltd. These units will ensure we can complete this project in the time scale of the grant. Total = \$12,843

*Consumables (total = \$12,956)*

We require \$12,956 for consumables so that we can take perform the experiment. Oral glucose tolerance tests, blood sampling kits and ELISA kits to analyse the hormones and proteins within the blood (including: insulin, HIF, HSP70, nitrate, nitrite, ghrelin, leptin, IL6, IL10, SOD and TNFa). Continuous glucose monitors will also be utilised to assess glucose concentrations. We have access to GENEActiv accelerometers, as such we are not asking for funds.

*Participant travel (total = \$652)*

Our patient and public involvement group (PPI) were clear that funds for travel needed to be supported. In line with our other trials we will provide £10 per visit to cover the costs of transport (£10 x 3 visits x 15 people = £450 or \$652).

17.2 Service Support Costs

17.3 Excess Treatment Costs

17.4 Study Sponsorship

This study is being sponsored by the UoP.

**18. TIMETABLE AND ORGANISATIONAL CHART**

[figure not shown]

Figure 1 shows the suggested timeline for the project.

**19. RESOURCES, EQUIPMENT AND PHYSICAL FACILITIES**

The Extreme Environments Laboratory at the University of Portsmouth has a 30 year history of conducting innovative human research trials. The laboratory contains some of the world's leading facilities for conducting environmental research including three bespoke environmental chambers, with temperature, humidity, solar, wind and hypoxia control, and a research group involving over 20 academics and researchers. The Institute of Biological and Biomedical Sciences at the University of Portsmouth has state of the art laboratories to enable us to analyse our biological samples. As well as the bespoke chambers, it hosts portable kit essential for this study such as two hypoxic generators (cloud 9), SpO2 monitors (Equivital EQ02, Hidalgo, UK) and accelerometers.

## **20. DISSEMINATION AND OUTCOME**

Results (estimates of effect sizes and confidence intervals) from this pilot study will be utilised to define our primary outcome and to power a larger, definitive multi-centre randomised control trial with our co-applicants and collaborators around Europe. Once our final report has been submitted to the funder, we will apply for NIHR funding via a researcher-led Research for Patient Benefit (RfPB) or an Efficacy and Mechanism Evaluation (EME) bid (depending on the effect size and sample size). The results will be disseminated through publication in peer-reviewed scientific and clinical journals and via presentations, local, national and international meetings. A summary of the results will be sent to all the participants. Finally, an open day and presentation will be carried out where the participants will be informed of the study findings and have the opportunity to ask any pertinent questions and/or provide feedback.

